9.1.7 Documentation of Concomitant Medications

Concomitant medication is any drug given in addition to the study drug. These may be prescribed by a physician or obtained by the subject over the counter. Concomitant medication is not provided by Takeda. At each study visit, subjects will be asked whether they have taken any medication other than the study drug (used from the start of the Run-in Period [Week 2] through the end of the study), and all medication including vitamin supplements, OTC medications, and oral herbal preparations, must be recorded in the eCRF.

If the concomitant medications are antihypertensive drugs, the daily dosage and unit of concomitant medications must be recorded in the eCRF as well.

9.1.8 Documentation of Concurrent Medical Conditions

Concurrent medical conditions are those significant ongoing conditions or diseases that are present at signing of informed consent. This includes clinically significant laboratory, ECG, or physical examination abnormalities noted at the first test after signing of informed consent. The condition (i.e., diagnosis) should be described.

9.1.9 Procedures for Clinical Laboratory Samples

All samples will be collected in accordance with acceptable laboratory procedures. The maximum volume of blood at any single visit is approximately 8 mL.

Table 9.a Clinical Laboratory Tests

Hematology	Chemistry	Urinalysis
Red blood cell count	Hemoglobin A1C/Hemoglobin (a)	Qualitative tests for glucose, pH, protein, occult blood, Ketones
White blood cell count with differential (neutrophils, basophils, eosinophils, lymphocytes, monocytes)	ALT Albumin Alkaline phosphatase (ALP) AST Bilirubin (Total bilirubin)	Quantitative tests for protein, creatinine, Albumin
Hemoglobin	Blood urea nitrogen (BUN) (b)	Protein/creatinine ratio, albumin/creatinine ratio, specific gravity
Hematocrit	Calcium	
Platelets	Chloride (b) Creatinine (b) Creatine kinase Cystatin C Glomerular Filtration Rate (b) Gamma-glutamyl transferase (GGT) Glucose Cholesterol (Total cholesterol) Triglyceride Phosphate Potassium (b) Sodium (b) Protein (Total protein) Lactate dehydrogenase (LDH)	
Other		
Urine qualitative human chorionic gonadotropin (hCG) pregnancy test (only female subjects of childbearing potential)		

(a) Only patients with diabetes mellitus

(b) Only the laboratory tests associated with renal function. The local laboratory will perform the laboratory tests associated with renal function in addition to measuring at the central laboratory to confirm the tolerability when TAK-536 is titrating (including unscheduled visit), if needed at the investigator's discretion.

The central laboratory will perform laboratory tests for hematology, chemistries, and urinalysis (acceptable under the fed condition).

The local laboratory will perform the laboratory tests associated with renal function (BUN, chloride, creatinine, eGFR, potassium, and sodium) in addition to measuring at the central laboratory to confirm the tolerability when TAK-536 is titrating (including unscheduled visit), if needed at the investigator's discretion. The results of the local measurements will not be required recording in the eCRF.

The following formula proposed by the Committee for Pediatric Chronic Kidney Disease will be used to deduce eGFR in Japanese children.

eGFR in children (mL/min/1.73 m²)
=110.2 × standard serum Cr (mg/dL)/serum Cr (mg/dL) + 2.93,

where, the standard serum Cr (mg/dL) is calculated from the height (Ht, in meter; Ht measured most recently will be used) as follows:

For a boy, $-1.259 Ht^5 + 7.815 Ht^4 - 18.57 Ht^3 + 21.39 Ht^2 - 11.71 Ht + 2.628$

For a girl, $-4.536 Ht^5 + 27.16 Ht^4 - 63.47 Ht^3 + 72.43 Ht^2 - 40.06 Ht + 8.778$

Uemura O, et al. Clin Exp Nephrol. 2014 [14]

Follow-up laboratory tests should be performed to determine whether the subject continue the study or not, in case of acute deterioration of renal function (eg, $\geq 50\%$ reduction in eGFR or less than 30 mL/min/1.73 m² or serum potassium value over 5.5 mEq/L) (See Section 7.5).

If subjects experience ALT or AST $> 3 \times$ ULN after the start of the Run-in Period (Week -2), follow-up laboratory tests (at a minimum, ALP [serum], ALT, AST, bilirubin [total bilirubin], GGT, and INR) should be performed within a maximum of 7 days and preferably within 48-72 hours after the abnormality was noted (Please refer to Section 7.5 for discontinuation criteria, and Section 10.2.3 for the appropriate guidance on Reporting of Abnormal Liver Function Tests in relation to ALT or AST $> 3 \times$ ULN in conjunction with total bilirubin $> 2 \times$ ULN.).

If the ALT or AST remains elevated $> 3 \times$ ULN on these 2 consecutive occasions the investigator must contact the Medical Monitor for consideration of additional testing, close monitoring, possible discontinuation of study drug, discussion of the relevant subject details and possible alternative etiologies. The abnormality should be recorded as an AE (please refer to Section 10.2.3 Reporting of Abnormal Liver Function Tests for reporting requirements).

Only female subjects of childbearing potential, defined by the investigator's or subinvestigator's positive opinion about the subject's reproductive potential, will undergo a qualitative hCG pregnancy test. The local laboratory will perform the test.

The investigator or subinvestigator is reviewing and filing the laboratory results. The investigator will maintain a copy of the normal reference ranges including the archival records for the laboratory used.

9.1.10 Contraception and Pregnancy Avoidance Procedure

From signing of informed consent, throughout the duration of the study, and for 1 month after the end of the study, female subjects of childbearing potential* who are sexually active with a nonsterilized male partner** must use adequate contraception. In addition they must be advised not to preserve or donate ova during this period.

*Females NOT of childbearing potential are defined as those who have been surgically sterilized (hysterectomy, bilateral oophorectomy or tubal ligation), who are postmenopausal (defined as at least 5 years since last regular menses, confirmed before any study drug is implemented), or who have no possibility of childbearing in the opinion of investigator or subinvestigator.

**Sterilized males should be at least 1 year postvasectomy and have confirmed that they have obtained documentation of the absence of sperm in the ejaculate.

An acceptable method of contraception is defined as one that has no higher than a 1% failure rate. In this study, female subjects of childbearing potential must use copper intrauterine devices (IUDs) combined with male condom or female condom. Medications and devices containing hormones are excluded.

The subject and the subject's parent, or the subject's legal guardian will be provided with information on acceptable methods of contraception as part of the subject informed consent/assent process and will be asked to sign a consent/assent form stating that they understand the requirements for avoidance of pregnancy, preservation or donation of ova from providing the consent/assent until 1 month has passed from the end of the study.

During the course of the study, regular urine hCG pregnancy tests will be performed only for female subjects of childbearing potential and subjects will receive continued guidance with respect to the avoidance of pregnancy as part of the study procedures (Appendix A).

This protocol does not condone or endorse under-age sexual activity.

9.1.11 Pregnancy

If any subject is found to be pregnant during the study she should be withdrawn and any sponsor-supplied drug should be immediately discontinued.

If the pregnancy occurs during administration of active study drug, or within 1 month of the last dose of active study drug, the pregnancy should be reported immediately, using a pregnancy notification form, to the contact listed in attachment 1.

If the female subject and her parent, or the subject's legal guardian agree to the primary care physician being informed, the investigator or subinvestigator should notify the primary care physician that the subject was participating in a clinical study at the time she became pregnant and provide details of treatment the subject received (blinded or unblinded, as applicable).

All pregnancies in subjects on active study drug will be followed up to final outcome, using the pregnancy form. The outcome, including any premature termination, must be reported to the sponsor. An evaluation after the birth of the child will also be conducted.

9.1.12 ECG Procedure

A resting 12-lead ECG will be recorded. The investigator (or a qualified observer at the study site) will interpret the ECG using 1 of the following categories: normal or abnormal. The investigator (or a qualified observer at the study site) will judge if it is clinically significant. The following parameters will be recorded on the eCRF from the subject's ECG trace: heart rate, RR interval, PR interval, QT interval, and QRS interval.

QTc will be calculated by the sponsor using the Fredericia's formula ($QT/RR^{0.33}$).

9.1.13 Pharmacokinetic Sample Collection

According to the study schedule (Appendix A), all pharmacokinetic samples should be collected on each visit except for Week 16, at the same time of blood sample collection for laboratory tests

to evaluate the trough values (approximately 21 to 27 hours after the latest dose) without taking the study drugs.

In addition to collection of the pharmacokinetic samples at trough, pharmacokinetic samples will be also collected once (total twice before and after the administration of the study drug) 2 hour (acceptable time window, 1 to 3 hours) after taking the study drug from the available subjects to evaluate the pharmacokinetics after taking the study drug at each visit by Week 12 of the Treatment Period.

On the visit of Week 16, subjects should visit the study site after taking the study drug to collect pharmacokinetic samples 2 hour (acceptable time window, 1 to 3 hours) after taking the study drug at the same time as the blood sample collection for laboratory tests.

9.1.13.1 Collection of Plasma for Pharmacokinetic Sampling

Blood samples (one 2-mL sample per scheduled time) for pharmacokinetic analysis of TAK-536 and its metabolites (M-I and M-II) will be collected into vacutainers containing ethylenediaminetetraacetic acid dipotassium salt dihydrate (EDTA-2K). After mixing the vacutainers 5 to 6 times by inversion immediately, vacutainers will be centrifuged at 4°C and 3000 rpm for 10 minutes. The plasma will be dispensed from the vacutainers to polypropylene tube and be stored frozen below -20°C in a freezer until being shipped to the analytical institute.

For each sample, the date and time of the latest study drug administration and the actual time of blood sample collection will be recorded in the eCRF.

9.1.13.2 Bioanalytical Method

Plasma concentrations of TAK-536 and its metabolites (M-I and M-II) will be measured by HPLC/MS/MS (high-performance liquid chromatography with tandem mass spectrometry) at PPD

9.1.14 Documentation of Subjects Failure

An eCRF must be created for all subjects giving informed consent who withdrawn before the start of the Treatment Period.

The primary reason for subject failure is recorded in the eCRF using the following categories:

- Death
- Adverse Event
- Screen Failure (failed inclusion criteria or did not meet exclusion criteria)
- Protocol deviation.
- Lost to follow-up.
- Withdrawal by subject <specify reason>.
- Withdrawal by parent or guardian <specify reason>.

- Study terminated by sponsor.
- Pregnancy
- Other <specify reason>.

Subject numbers assigned to subjects who fail screening should not be reused.

9.1.15 Documentation of Study Entrance

Only subjects who meet all of the inclusion criteria and none of the exclusion criteria are eligible for entrance into the Treatment Period.

If the subject is found to be not eligible for the Treatment Period, the investigator or subinvestigator should record the primary reason for failure on the applicable eCRF.

9.2 Monitoring Subject Treatment Compliance

Compliance with study drug (amount of dispense and return) between the visits, timing of the study dose (before or after breakfast) and the latest dosing date and time before collecting sample for pharmacokinetic evaluation will be confirmed and recorded in the eCRF.

Subjects, the subjects' parent, or the subjects' legal guardian will be instructed to be compliant with the study drug throughout the study. If a subject is noncompliant (< 70% or > 130%) with the study medication (TAK-536 placebo) during the Run-in Period, the subject will be excluded before the start of the Treatment Period, as indicated in the exclusion criteria No. 5. If a subject is noncompliant with the study medication (TAK-536) (eg, failure to take < 50% of the scheduled doses after the last visit) after the start of the Treatment Period, it may be appropriate to withdraw the subject from the study. All subjects should be reinstructed about the dosing requirement during study contacts. The authorized study personnel conducting the re-education must document the process in the subject source records.

9.3 Schedule of Observations and Procedures

The schedule for all study-related procedures for all evaluations is shown in Appendix A. Assessments should be completed at the designated visit/time points.

9.3.1 Screening

Subjects will be screened within 14 days prior to the start of the Run-in Period. Subjects will be screened in accordance with predefined inclusion and exclusion criteria as described in Section 7.0.

9.3.2 Start of the Run-in Period (Week -2)

The study drug (TAK-536 placebo) for the Run-in Period will be administered on the same day after the tests, observations and evaluations specified for each visit are performed. In case that subjects take RAS inhibitors in the morning of the visit day, the administration of the study drug (TAK-536 placebo) for the Run-in Period will be started from the next day.

Two weeks will be set as the Run-in Period. The subjects whose blood pressures meet the inclusion criteria 1 week (at earliest) after receiving placebo during the Run-in Period can enter the Treatment Period. For the subjects only who treated with any antihypertensive drugs as a prior treatment, the Run-in Period could be extended up to 4 weeks if blood pressures do not meet the inclusion criteria.

9.3.3 End of the Run-in Period (Week 0)

Subjects meeting all of the inclusion criteria and none of the exclusion criteria will be entered after performing the tests and observations specified for each visit and will be initiated to receive the study drug for the Treatment Period on the same day.

The first and the last date of the study drugs administration for the Run-in Period will be recorded in the eCRF for those receiving the study drugs for the Run-in Period and subsequently received the study drug for the Treatment Period.

See Section 9.1.14 for procedures for documenting subjects withdrawn before the start of the Treatment Period.

9.3.4 Treatment Period (Weeks 2, 4, 8, 12, 16, 20, 24, 32, and 40)

The tests and observations specified for each visit will be performed.

Between the visits of Week 4 and 8 during the Treatment Period I, an additional unscheduled visit of Week 6 may be requested at the investigator's discretion in order to titrate the dose of the study drug in the subjects when the further decrease in blood pressure is needed.

On the visit of Week 16, subjects should visit the study site after taking the study drug and the tests and observations specified will be performed.

9.3.5 Final Visit or Early Termination

The Final Visit will be performed on Week 52 or at the Early Termination Visit.

The tests and observations specified for each visit will be performed.

For subjects early terminate the study after the start of the Treatment Period, if possible, the same tests, observations, and evaluations as those scheduled at Week 52 should be performed.

Whenever possible, office sitting blood pressure should be determined within 3 days after early termination and the other tests, observations, and evaluations should be performed within 14 days after early termination (the next day of the final dose should be calculated as the first day).

For all subjects who entered the Treatment Period, the investigator or subinvestigator must complete the Subject Status on eCRF page with the first day when the subjects received the study drug for the Treatment Period and study completion or early termination status until Week 24 and study completion status at Week 52 for subjects who continuingly received the study drug beyond Week 24.

9.3.6 Follow-up Period: Week 54

Follow-up Period will begin the first day after the final administration of TAK-536 for the Treatment Period and will continue until 2 weeks. The tests and observations specified for each visit will be performed. If subjects terminate the study drug in the Run-in Period or at an early stage of the Treatment Period, no tests, observations, and evaluations will be required but care should be taken for subject safety.

9.3.7 Post Study Care

The study drug will not be available upon completion of the subject's participation in the study. The subject should be returned to the care of a physician and standard therapies as required.

10.0 ADVERSE EVENTS

10.1 Definitions

10.1.1 AEs

An AE is defined as any untoward medical occurrence in a clinical investigation subject who has signed informed consent to participate in a study; it does not necessarily have to have a causal relationship with this treatment or study participation.

An AE can therefore be any unfavorable and unintended sign (eg, a clinically significant abnormal laboratory finding), symptom, or disease temporally associated with the study participation whether or not it is considered related to the drug or study procedures.

10.1.2 Additional Points to Consider for AEs

An untoward finding generally may:

- Indicate a new diagnosis or unexpected worsening of a pre-existing condition. (Intermittent events for pre-existing conditions or underlying disease should not be considered AEs.)
- Necessitate therapeutic intervention.
- Require an invasive diagnostic procedure.
- Require discontinuation or a change in dose of study drug or a concomitant medication.
- Be considered unfavorable by the investigator or subinvestigator for any reason.
- AEs caused by a study procedure (eg, a bruise after blood draw) should be recorded as an AE.

Diagnoses vs signs and symptoms:

- Each event should be recorded to represent a single diagnosis. Accompanying signs (including abnormal laboratory values or ECG findings) or symptoms should NOT be recorded as additional AEs. If a diagnosis is unknown, sign(s) or symptom(s) should be recorded appropriately as an AE(s).

Laboratory values and ECG findings:

- Changes in laboratory values or ECG parameters are only considered to be AEs if they are judged to be clinically significant (i.e., if some action or intervention is required or if the investigator or subinvestigator judges the change to be beyond the range of normal physiologic fluctuation). A laboratory re-test and/or continued monitoring of an abnormal value are not considered an intervention. In addition, repeated or additional noninvasive testing for verification, evaluation or monitoring of an abnormality is not considered an intervention.
- If abnormal laboratory values or ECG findings are the result of pathology for which there is an overall diagnosis (eg, increased creatinine in renal failure), the diagnosis only should be reported appropriately as an AE.

Pre-existing conditions:

- Pre-existing conditions (present at the time of signing of informed consent) are considered concurrent medical conditions and should NOT be recorded as AEs. Baseline evaluations (eg, laboratory tests, ECG, X-rays etc.) should NOT be recorded as AEs unless related to study procedures. However, if the subject experiences a worsening or complication of such a concurrent medical condition after informed consent is signed, the worsening or complication should be recorded appropriately as an AE. The investigator or subinvestigator should ensure that the event term recorded captures the change in the condition (eg, “worsening of ...”).
- If a subject has a pre-existing episodic condition (eg, asthma, epilepsy) any occurrence of an episode should only be captured as an AE if the episodes become more frequent, serious or severe in nature, that is, the investigator or subinvestigator should ensure that the AE term recorded captures the change in the condition from Baseline (eg “worsening of...”).
- If a subject has a degenerative concurrent medical condition (eg, cataracts, rheumatoid arthritis), worsening of the condition should only be captured as an AE if occurring to a greater extent to that which would be expected. Again, the investigator or subinvestigator should ensure that the AE term recorded captures the change in the condition (eg, “worsening of ...”).

Worsening of AEs:

- If the subject experiences a worsening or complication of an AE after starting administration of the study drug, or if a sign or a symptom appears secondarily due to an AE, the worsening or complication should be recorded appropriately as a new AE. The investigator or subinvestigator should ensure that the AE term recorded captures the change in the condition (eg, “worsening of...”).
- If the subject experiences a worsening or complication of an AE after any change in the study drug, or if a sign or a symptom appears secondarily due to an AE, the worsening or complication should be recorded as a new AE. The investigator or subinvestigator should ensure that the AE term recorded captures the change in the condition (eg, “worsening of...”).

Changes in severity of AEs:

- If the subject experiences changes in severity of an AE that are not related to starting the study drug or changing in the dose or regimen, the event should be captured once with the maximum severity recorded.

Preplanned surgeries or procedures:

- Preplanned procedures (surgeries or therapies) that were scheduled prior to signing of informed consent are not considered AEs. However, if a preplanned procedure is performed early (eg, as an emergency) due to a worsening of the pre-existing condition, the worsening of the condition should be captured appropriately as an AE. Complications resulting from any planned surgery should be reported as AEs.

Elective surgeries or procedures:

- Elective procedures performed where there is no change in the subject's medical condition should not be recorded as AEs, but should be documented in the subject's source documents. Complications resulting from an elective surgery should be reported as AEs.

Insufficient clinical response (lack of efficacy):

- Insufficient clinical response, efficacy, or pharmacologic action, should NOT be recorded as an AE. The investigator or subinvestigator must make the distinction between exacerbation of pre-existing illness and lack of therapeutic efficacy.

Overdose:

- Cases of overdose with any medication without manifested side effects are NOT considered AEs, but instead will be documented on an Overdose page of the eCRF. Any manifested side effects will be considered AEs and will be recorded on the AE page of the eCRF.

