6.2 Justification for Study Design, Dose, Regimen, and Endpoints

[Justification for the Study Design]

Many pediatric patients with renal dysfunction are assumed to be entered this study since the proportion of pediatric patients with secondary hypertension caused by renal disease is high in pediatric patients with hypertension. Evidence-based Clinical Practice Guideline for CKD 2013 (JSN2013) [9] indicates that treatment with ARB should be start at a low dose in patients with renal dysfunction and the dose should be increased with caution by confirming the hypotensive effect of ARB and renal function. On the basis of above indication, an open-label, optional titration

design was selected in this study, in which TAK-536 can be titrated with monitoring subject condition.

Co-administration of RAS inhibitors, which is similar to TAK-536, is prohibited in order to evaluate appropriately the efficacy of TAK-536 in the pediatric patients throughout the Run-in Period and the Treatment Period I. In consideration of the safety for vulnerable pediatric population, subjects can continue to receive a single antihypertensive drug other than RAS inhibitors in the same dosage after the start of the Run-in Period, if the subjects are considered to need the additional treatment for hypertension by the investigator or subinvestigator. In the Treatment Period II, the subjects whose blood pressure is not reduced sufficiently by TAK-536 can receive additional antihypertensive drugs other than RAS inhibitors concomitantly in order to evaluate the efficacy and safety of the long-term administration of TAK-536 in pediatric patients under the condition of being closer to the routine medical care.

The Run-in Period with placebo was selected to wash out the placebo effect of the study drug and the influence of antihypertensive drugs as a prior treatment in subjects who were treated with any prior antihypertensive drugs. In addition, the Run-in Period allows the opportunity to assess subject compliance with the study drug (i.e., placebo) and subjects who are not sufficiently compliant with placebo will be excluded.

The Follow-up Period was selected to evaluate the subject safety after the study drug administration.

[Justification for the Doses]

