10.2.1.3 AEs of Special Interest Reporting

Pediatric subjects, the subject population of this study, are vulnerable, and as such need special attention with regard to the risk of the over decrease in blood pressure accompanying the use of antihypertensive drugs. Furthermore, kidney function is often impaired in pediatric subjects with secondary hypertension. Administration of RAS inhibitors to such patients may reduce GFR, deteriorating the kidney function. Hence, the following adverse events related to hypotension or renal impairment will be investigated as special interest AEs in this study.

[Hypotension-related AE]

Hypotension, blood pressure decreased, orthostatic hypotension, blood pressure orthostatic decreased, dizziness, dizziness postural, vertigo, circulatory collapse, shock, loss of consciousness, syncope, and presyncope.

[Renal dysfunction-related AE]

Renal failure, acute renal failure, renal impairment, prerenal failure, acute prerenal failure, anuria, oliguria, nephropathy toxic, acute phosphate nephropathy, and azotaemia.

If this AE of special interest occurs during the Run-in Period, the Treatment Period or the Follow-up Period, it should be reported to the sponsor (described in the separate contact information list) immediately or within 1 business day of first onset or subject's notification of the event. Hypotension-related AE or renal dysfunction-related AE Form or an SAE Form should be completed, signed and/or sealed by the principal investigator, and reported to appropriate personnel in the separate contact information list within 10 business days.

The AE of special interest have to be recorded as AEs in the eCRF. An evaluation form along with all other required documentation must be submitted to the sponsor.

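### The AE rules do not settle whether worsening of pre-existing CKD is recorded, so renal AE incidence may be understated, and the categorical laboratory tables can miss a large fall in eGFR from baseline

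*Protocol*

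**What the plan says.** Protocol 10.1.2 addresses worsening of a pre-existing condition in three places.

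- The opening list of what an untoward finding may do includes "Indicate a new diagnosis or unexpected worsening of a pre-existing condition".
- The general rule on pre-existing conditions says that if such a condition worsens "after informed consent is signed, the worsening or complication should be recorded appropriately as an AE". It has no expectation test.
- A later bullet begins "If a subject has a degenerative concurrent medical condition (eg, cataracts, rheumatoid arthritis" and says that "worsening of the condition should only be captured as an AE if occurring to a greater extent to that which would be expected". It does not name CKD and does not say who decides what is expected, or against what.

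The same section says of laboratory findings: "Changes in laboratory values or ECG parameters are only considered to be AEs if they are judged to be clinically significant". Where an overall diagnosis explains an abnormal value, only the diagnosis is reported.

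On the population, Protocol 6.2 states that "Many pediatric patients with renal dysfunction are assumed to be entered this study" and that TAK-536 has not been given to hypertensive children with renal dysfunction. Protocol 10.2.1.3 explains why renal events are of special interest: "Administration of RAS inhibitors to such patients may reduce GFR, deteriorating the kidney function". It lists renal terms, requires them to be recorded as AEs, and asks for a report to the sponsor within 1 business day. SAP 7.11.1.2 builds the renal-dysfunction TEAE table from the preferred terms in SAP Table 9.b.

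Laboratory tests are part of the primary safety endpoint in their own right (Protocol 13.1.5). SAP 7.11.2.1 provides observed values, changes, case plots, normal-range shift tables and markedly abnormal value (MAV) counts.

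**The concern.** The event that the protocol singles out as the renal risk of this drug class is loss of kidney function in children whose kidneys are already impaired. That is also the event for which the recording rule is unclear. If an investigator reads CKD as a degenerative condition, a decline judged to be in line with its natural course is not an AE. It then has no AE record, severity grade or causality assessment, does not enter the renal TEAE table, and does not prompt a special-interest report. This omission can only lower the renal AE count.

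The decision would also rest on many separate judgements. Fifty children at about 25 sites is an average of two per site, and the protocol offers no common standard for expected progression. An AE is defined in Protocol 10.1.1 without regard to cause, and 10.1.6 provides a separate causality assessment. An expectation filter at the recording step brings part of that judgement forward to a point where it leaves no trace.

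**Working it through.** The documents state no figure for this point. The check is a comparison of the rules, followed by arithmetic on the laboratory limits.

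**1. Three readings of one case: CKD present at consent, renal function declines on treatment**

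| Rule in Protocol 10.1.2 | Test applied | Recorded as an AE? |
|---|---|---|
| General rule, pre-existing conditions | Any worsening after consent | Yes |
| Opening list | Refers to unexpected worsening | Unclear |
| Degenerative conditions | Only worsening beyond what is expected | Only if the investigator thinks so |

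The laboratory route does not resolve this. A creatinine rise judged clinically significant is an AE, but if a diagnosis explains it, only the diagnosis is reported. When that diagnosis is the pre-existing CKD, the question returns to the table above.

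**2. Special-interest lists**

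Neither the list in Protocol 10.2.1.3 nor SAP Table 9.b has a term for worsening of CKD, creatinine increased or GFR decreased. Renal impairment and renal failure are on both. A recorded decline therefore reaches the renal table only if it is reported under a term that codes to the list.

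**3. What the laboratory tables would show**

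Inputs:

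- MAV limits of eGFR < 30 and creatinine > 2.0 mg/dL (SAP Table 9.c).
- A 50% eGFR reduction, or eGFR below 30, as the criterion for follow-up tests and, if seen at 2 consecutive time points, for considering discontinuation (Protocol 9.1.9 and 7.5).
- Baseline values of 45, 60 and 90, which are assumptions because the documents give no eGFR distribution.

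Percentage fall = (baseline − later value) / baseline.

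| Baseline | Later value | Fall | eGFR MAV (< 30)? | 50% or < 30 criterion? |
|---|---|---|---|---|
| 45 | 30 | 15/45 = 33% | No | No |
| 60 | 31 | 29/60 = 48% | No | No |
| 90 | 46 | 44/90 = 49% | No | No |

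The creatinine limit catches some of these. Rearranging the formula in Protocol 9.1.9, creatinine = 110.2 × standard creatinine / (eGFR − 2.93). At eGFR 31:

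- Height 1.30 m: boy 110.2 × 0.402 / 28.07 = 1.58; girl 110.2 × 0.393 / 28.07 = 1.54. Not flagged.
- Height 1.45 m: boy 1.90; girl 1.83. Not flagged.
- Height 1.60 m: boy 2.37; girl 2.21. Flagged.

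So the 60-to-31 fall escapes both limits in boys shorter than about 1.49 m and girls shorter than about 1.52 m. For the 90-to-46 fall at 1.60 m, creatinine is 1.54 (boy) and 1.44 (girl), which is not flagged. The BUN and potassium limits could still be met; they are not functions of eGFR and cannot be computed from it.

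**4. Shift tables**

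The categories are below, within and above the normal range. A child already below the range at Week 0 who falls further stays in the same cell. The documents give no eGFR reference range, so this assumes that its lower limit lies above the child's baseline value.

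**The case against.** The strongest reply is that the degenerative-condition bullet gives cataracts and rheumatoid arthritis as its examples and never mentions CKD. The general rule a few lines above it has no expectation test, so on a plain reading worsening CKD is recorded. The opening list is illustrative: it says what a finding generally may do, and other items in it cover findings that require a dose change or that the investigator considers unfavorable for any reason. This stands in part. The default does favour recording, and applying the narrower bullet to CKD is an inference. It is an available inference, though: Protocol 4.1 itself describes CKD as progressing, and nothing excludes CKD from the bullet.

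A second reply is that central-laboratory renal values are collected and analysed as a primary endpoint whether or not an AE is recorded. That is correct and limits the point considerably. A reader might infer that a renal decline could vanish from the study. The documents do not support that: it would be visible in the change summaries and case plots. What could be lost is the AE record, its causality and seriousness assessment, and prompt reporting.

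A reader might also infer that the missing control arm causes the problem. It does not. A comparator helps to attribute a decline to drug or disease at group level; it would not tell an investigator what to expect in one child at the time of the event, nor prevent the event being recorded.

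**Conclusion.** The inconsistency in Protocol 10.1.2 is real and bears on a primary safety endpoint. Renal AE incidence may be understated, in one direction only, and special-interest reporting may be missed. The laboratory data limit the harm but do not remove it, because the SAP has no category for a fall in eGFR relative to baseline.

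The size cannot be estimated. Protocol 4.1 gives renal disease as the cause of 60% to 80% of secondary hypertension in children, but no document gives the share of enrolled children with secondary hypertension, the rate of renal worsening, or how often it would be judged expected. A reader might be tempted to multiply guesses for these; the answer would be the guesses. If every investigator follows the general rule, the loss is zero. In a safety set of 50, each omitted child is 1/50 = 2 percentage points.

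The conclusion assumes that at least some investigators could read CKD as degenerative. The laboratory illustrations rest on the assumed baselines and heights above. A reader might extend the argument to the hypotension-related events; nothing here supports that. This is a clarification worth making at little cost, not a threat to the validity of the study.

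**What to change.** 1. Add to Protocol 10.1.2: *The exception for expected worsening does not apply to renal function. Clinically significant worsening of renal function, including worsening of pre-existing CKD, is recorded as an AE and reported under 10.2.1.3 for the periods which that section covers. Whether the worsening was expected is considered only in the causality assessment.*
2. Add matching terms (worsening of chronic kidney disease, creatinine increased, GFR decreased) to the renal list in Protocol 10.2.1.3 and to SAP Table 9.b. Without this, newly recorded events need not reach the renal TEAE table.
3. Add to SAP 7.11.2.1 a table of subjects by percentage fall in eGFR from Week 0, by visit and for the largest fall on treatment, whether or not an AE was recorded. Fix the cut-points before database lock. Include 50%, which the protocol already uses, and at least one lower value.

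The cost is one protocol sentence, a note to sites, two list changes and one table. The downside is that some natural CKD progression will be counted as AEs, with causality recorded separately, and investigators still judge clinical significance. Items 1 and 2 concern recording and reporting only and change no dose or stopping rule. Item 3 uses central-laboratory data that are collected in any case, so it helps even where AE recording cannot be corrected after the event.
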